7.1 Eligibility of trial participants

7.1.1 Trial participant inclusion criteria

1. Volunteers without clinical evidence of COVID-19 infection aged 18 years and older
2. Participants who are at high risk of SARS-CoV-2 infection, defined as adults whose locations or circumstances put them at appreciable risk of exposure to SARS-CoV-2 and COVID-19. (see country specific addendum if needed to define further)
3. The participant must have a mobile phone and access to the Internet for data collection purposes.
4. Participants who are willing and able to provide informed consent via an electronic consent process.

7.1.2 Trial participant exclusion criteria

Exclusion criteria (these could be modified depending on the choice of interventions in the platform trial)

1. Weight outside range 50 kg – 120 kg (110 lbs – 265 lbs).
2. Prior enrolment into this or other COVID-19 interventional prevention or treatment trials (observational trials not excluded).
3. Self-reported or laboratory confirmed previous or current diagnosis of SARS-CoV-2 or COVID-19.
4. Self-reported current acute respiratory infection.
5. Concurrent and/or recent use of the investigational product/s, a product considered to be equivalent to the investigational product/s, or any other product that is likely to interfere with the investigational products in this trial or the interpretation of the trial data.
6. Self-reported known allergies to any of the IMPs and excipients of the IMPs and placebo.
7. Self-reported presence or history of the conditions listed in the appendix relevant to that IMP
8. Self-reported current use of medication with known to interact with any of the medications listed in the appendices.
9. Inability or unwillingness to be followed up for the trial period.

Additional to the set of exclusions in the core protocol, each arm of the trial (e.g. “MR vs Placebo” arm or “MMR vs Placebo” arm) will have their own set of additional exclusion criteria (refer to the appendix). Participants will only be randomized to those arms for which they are eligible.

7.2 Recruitment

Each region will adopt an approach that is appropriate for enrolment according to local conditions, and one that is in compliance with its IRB/REC and national regulatory body guidelines. Recruitment may include advertisements (via posters, emails and social media messages at each site) that will alert relevant potential at risk participants to the study. Participants will self-identify and self-enrol by reading the participant information sheet (PIS) and then offering electronic informed consent through an online website using computer or smartphone. Participants will be asked to confirm their eligibility, i.e. that they meet all the inclusion criteria and that they do not meet any of the exclusion criteria. Formal verification based on participant responses will be needed by the site PI of the suitability of the proposed participant.

Participant recruitment at a site will only commence when the trial has:

- Been initiated by the Sponsor (or the delegated representative), and
- Issued with the ‘Open to Recruitment’ letter.

7.3 Informed consent procedure

Informed consent procedures will be implemented in accordance with local IRB/IEC and national regulatory authority requirements. The participant must sign the approved version of the informed consent form online before any study specific procedures are performed. See country-specific addenda for further details on site-specific procedures and documents.

The online participant information will be presented and will detail the exact nature of the study, what it will involve for the participant, the implications and constraints of the protocol, the known side effects and risks involved in taking part. Additional consent may be sought for long-term sample storage in selected jurisdictions. This will be detailed in the country-specific addenda. All the site-specific participant information sheets (PIS) describe the safety issues associated with interventions as described in the relevant package inserts. It will be clearly stated that the participant is free to withdraw from the study at any time for any reason without prejudice to future care and with no obligation to give the reason for withdrawal.

For this trial, all consent will be obtained electronically after the participant has read the information. Given the urgency of the clinical question, the pressure under which staff members are working and the simplicity of the trial design, if a participant wishes to enrol online after reading the PIS, this will be permitted, unless specifically excluded in an individual country specific appendix, with the site PI able to remotely approve the application without physically examining the participant. The participant will be given as much time as wished to consider the information, and to question the PI and study team before they decide whether they will participate in the study. The consent process may be modified as required to meet local regulatory requirements.

The participant will confirm they have read the PIS via the consent form. It will be clearly stated that participants are under no obligation to enter the trial and that they can withdraw at any time during the trial, without having to give a reason. They will be asked for consent to access their medical records for study purposes should they become ill. No clinical trial procedures will be conducted prior to the participant giving consent by signing the electronic consent form. Consent will not denote enrolment into trial. The PIS and consent form will be reviewed and updated if necessary, throughout the trial (e.g. where new safety information becomes available) and participants will be re-consented as appropriate.

8 Trial procedures

Given the infectious nature of COVID-19, the traditional approach to trials will be adapted to data collection through telephone interviews or self-data collection. For this reason, we aim to ensure that all participant-reported data are collected through a combination of an online system and SMS messaging. See appendix 1 for the trial schedule of evaluations.

8.1 Screening / Pre-Enrolment Assessments

The following pre-enrolment assessments and procedures will be performed:

- The participant will be invited to view the trial website.
- Potential participants will be shown the participant information online and asked to complete a simple e-questionnaire to ensure that they understand the nature of the trial.
- If potential participants wish to speak to a member of the study team before giving consent, a mechanism will be offered for them to do so.
- Participants will be invited to offer consent online.

- They will be asked screening and eligibility questions. Eligibility will be confirmed by the online system based on the responses given.
- Participants will also confirm that they expect to continue to have a mobile phone and will have access to the Internet for the duration of the trial directly or indirectly (i.e. via local center in remote settings).
- Participants will be asked for details of at least one alternative contact in case they become sick and are unable to respond to the study team. This will allow the study team to find out what has happened
- If required by country legislation, the alternative contact person will be invited to confirm that they are prepared to be registered for this purpose within the trial in line with prevailing data security legislation.
- Site lead will confirm that the participant meets eligibility criteria through the online platform.
- A new case record will be created on the secure online platform. Basic demographic information and details of past medical history, concomitant medications, allergies, smoking, alcohol and other drug intake will be noted.
- Baseline samples will be collected for batched SARS CoV2 serology testing.
- Screening failures (i.e. participants who do not meet eligibility criteria at time of screening) will be allowed to be rescreened once.

See country-specific addenda for details on alternate contacts.

8.2 Enrolment / Randomization Procedures

Participant registration will be undertaken online using computer or smartphone.

Following participant consent, and confirmation of eligibility (see section 8.1 for pre-treatment assessments) the registration and randomization procedure described below will be carried out.

Coordinated on-line registration and allocation of participant trial numbers will be required to enrol participants. Blocked randomization list will be used to allocate study participants to one of the groups, stratified by age, study location. The lists will be created by the study statistician based at the UCL CCTU and will be implemented through the online randomization portal, supplied by Sealed Envelope Ltd.

Participants will be assigned to treatment groups through consecutive allocation of subject numbers, and the use of a Trial Subject Enrolment Log which will be stored on the Sealed Envelope system. Participants will only be randomized to arms that they are eligible for (refer to section 7.1 and relevant appendix).

Participants are considered to be enrolled into the trial following: consent, pre-treatment assessments (see section 8.1) including confirmation of eligibility, completion of the registration/randomization process, allocation of the participant trial number and treatment by the central coordinating team/remote system.

8.3 Procedure for Allocating Intervention/s

The site PI or designee will be notified when a new participant has joined the study. The site PI will satisfy themselves that the participant meets the study eligibility requirements. Once e-consent and PI verification are complete the participant can be randomized in the system and the unblinded pharmacist will be sent the treatment allocation. The local IMP supplier (usually the facility's pharmacy or a research pharmacy) will be alerted that a new participant has joined the study. IMP will be prescribed and prepared for the participant using a locally agreed standard operating procedure. Once the IMP is ready, it will be dispensed to the participant after verifying ID.

8.4 Dose Modifications

If an adverse event is recorded (see Section 9), the site PI or designee will be immediately alerted. If the site PI or designee deems that the adverse event is not related to the IMP and is therefore not an adverse reaction, and if the site PI or designee deems it safe for the participant to continue in the trial, the participant may continue to take the IMP, where relevant. If the site PI or designee deems it better for clinical reasons to stop taking the IMP, the participant should do so. No dose reductions or other modifications will be included in the trial.

8.5 Subsequent Assessments and Procedures

All participants will complete online questionnaires of symptoms, general well-being (and compliance with drug taking where relevant) at enrolment and then at days 30 and 60 and further timepoints up to 150 days after enrolment to the study. The system is currently expected to be supplied by Sealed Envelope Ltd, a UK company that stores data in the UK. At each time point, where relevant, participants will also be asked to confirm their current concomitant medication use. This study is taking place in individuals at a time of great concern about COVID-19 so we do not expect adherence will be a major challenge but as this is a pragmatic trial, the outcomes are likely to reflect real world drug adherence. If participants are aware that they are receiving placebo, adherence might be decreased. All efforts will be made to conceal the treatment allocation.

All participants will also receive an SMS message once a week to ask about their health. If relevant it will also remind them to take their study medications. The platform used is currently expected to be Telerivet Inc and will integrate with the Sealed Envelope system. Telerivet stores its data in EU data centers. If the participant does not respond for one week, the site PI or designee will be prompted to contact the participant. If the participant cannot be contacted, the site PI or designee will contact the alternate contacts provided (see section 8.1).

If a participant experiences symptoms consistent with COVID-19 they will be asked to register this on the online system. They will then be asked to complete an extra online questionnaire regarding symptoms, general well-being, and compliance with study product at the time of diagnosis. They will also be asked to confirm their current medication use. They will be prompted to undergo testing for active infection to confirm the COVID-19 diagnosis if this has not been done as part of their routine clinical care. We anticipate that the sequence of events will be that a participant experiences symptoms, reports those and is prompted to arrange or self-collect samples for testing for active infection. Those with a negative test and ongoing symptoms may need a second test. This may be collected from their routine health care provider. We plan to evaluate sample integrity under the storage/transport conditions we will be using to collect mid-nasal swab specimens or equivalent sample collection.^{13,14} Where feasible, we will attempt to quantify viral RNA in participants with SARS-CoV-2 infection. A confirmed diagnosis would then prompt additional follow up. Participants who receive a confirmed diagnosis elsewhere will be asked to register this online. Similar questions about symptoms and study product compliance will be assessed. Where a participant may undergo testing for active infection outside of the trial procedures, consent will be sought at baseline to enable research staff to access the data. In addition, permission will be sought at baseline to access other data sources such as hospital records and death records.

Dried blood spots will be collected from all participants to test for antibodies to SARS-CoV-2 at the time of entry, 60 days, and at 150 days when follow-up is completed.

For any woman who is pregnant on starting the study or becomes pregnant during the 60-day study primary outcome period, an assessment of pregnancy outcome will be conducted at 6 weeks post-partum.

See Appendix 1 for schedule of assessments.

8.6 Laboratory Assessments and Procedures

The primary outcome of the trial is symptomatic (i.e. any of the following: cough, shortness of breath or difficulty breathing, fever, chills, muscle pain, sore throat, new loss of taste or smell, nausea, vomiting, or diarrhea) COVID-19 infection confirmed by a RT-PCR test. This will be assessed in symptomatic participants by (self-collected) mid-turbinate nasal swab or equivalent if not otherwise collected for local clinical purposes. These have been shown to have equivalent sensitivity to health care worker collected nasopharyngeal (NP) swabs but faster, better tolerated, and with less potential for sneezing, coughing and gagging, than an NP swab.¹⁵ Depending on local circumstances, at enrolment participants may be provided with a pack which includes step-by-step instructions for sample self-collection. A swab plus viral transport medium (or saline) will be packaged together for ease of use. Participants will be advised to place the swab in the transport medium and to place the tube in a transport bag provided. If a participant prefers not to take their own swab they can seek assistance with sample collection at their nearest COVID-19 testing center or to their regular healthcare provider. We will describe the methodology and performance characteristics of the quantitative RT-PCR assay(s) used in this study in a laboratory analytical manual. Where feasible, we will attempt to quantify viral RNA when viral shedding is assessed in the nasal swab samples collected from participants with SARS-CoV-2 infection. RT-PCR testing will take place in the country of participation.

The purpose of serology is to provide additional information for **secondary analyses**. A sample collected at baseline will provide information on the proportion of participants exposed to infection prior to randomization. Given that optimization of serological assays is still underway, we will collect these samples for testing later. Details of testing will be specified in the laboratory manuals. Participants will be provided with the necessary equipment and instructions for obtaining dried blood spots (e.g. alcohol swab, lancet, filter paper). Each site will have a procedure for obtaining the dried blood spot specimens from participants. Sample processing and storage will be completed per site-specific standard operating procedures. The DBS might also to conduct serology for measles and rubella antibody titers to evaluate against immunization history and also because there are cases of reported primary vaccination failure.

Additional sampling and testing procedures will be detailed in country-specific addenda.

8.7 Clinical Procedures and Data Collection

Participants will respond to weekly SMS surveys in combination with secure CRF login to a self-report online system, to be completed monthly, with questions around symptoms, exposure and self-reported treatment adherence and SAEs.

If the participant becomes ill and is admitted to hospital, the study team may review the hospital records in line with hospital policies, and if the participant has consented to medical record access.

8.8 Assessment of IMP compliance

Adherence (where applicable) will be assessed at each monthly questionnaire along with weekly SMS prompts.

8.9 Discontinuation / withdrawal of participants

In consenting to participate in the trial, participants are consenting to trial treatment, assessments, follow-up and data collection. The importance of safety follow-up will be emphasized to the participant in the PIS. Each participant has the right to withdraw from the study at any time. If a participant

expresses their wish to withdraw from trial treatment, sites will seek permission to allow use of routine follow-up data from routine health records to be used for trial purposes. The participant may choose to decline this request.

The decision of the participant to withdraw from treatment will be recorded in the CRF/online database. The participant may withhold their reason for withdrawal however, if the participant gives a reason for their withdrawal, this will be recorded in the CRF/online database. If a participant explicitly states they do not wish to contribute further data to the trial their decision will be respected and recorded in the CRF/online database. Trial data already collected will not be deleted.

Additionally, a participant may be withdrawn from trial treatment whenever the site lead investigator considers it necessary. Reasons for discontinuing IMP may include:

- if the safety risk in an arm warrants discontinuation of all participants in that arm in the opinion of the Data Monitoring Committee (DMC);
- if the participant develops confirmed symptomatic COVID-19 they will stop the trial intervention where applicable;
- unacceptable toxicity; either self-reported or based on assessment by the site PI using grading tables;
- intercurrent illness which prevents further IMP administration;
- participants withdrawing consent to further trial treatment;
- any alterations in the participant's condition which justifies the discontinuation of IMP in the site investigator's opinion;
- persistent non-compliance to protocol requirements.

The decision to discontinue IMP, where applicable, must be recorded in the electronic CRF. For participants who remain in the trial for the purposes of follow-up for safety and / or data analysis, they will be managed according to the treatment arms to which they have been originally randomised.

Loss to follow-up

If a participant moves from the area where they started the study, every effort will be made for the participant to be followed up at another participating trial site and for this new site to take over the responsibility for the participant. If a participant is lost to follow-up at a site, efforts will be made to contact the participant's alternate contact or relevant laboratory, healthcare or hospital network (if the participant has given consent), to obtain information on the participant's status.

8.10 Replacements

Withdrawn participants will not be replaced.

8.11 Stopping Rules

The trial may be stopped before completion for the following reasons:

- On the recommendation of the DMC (see section 13).
- On the recommendation of the sponsors and CI.

If a safety trigger is reached safety data will be reviewed and a decision on continuation will be made by the DMC with input from the sponsor.

8.12 Definition of End of Trial

The expected duration of the trial is one year from recruitment of the first participant. The end of trial is five months after the last participant is enrolled when the database is locked, and all queries are

resolved. If further resources become available and the Trial Management Group (TMG) recommends continuation, the trial may be extended for up to two years from enrolment of the last participant.

9 Recording and reporting of adverse events and reactions

9.1 Definitions

Definitions of harm of the EU Directive 2001/20/EC Article 2 based on the principles of ICH GCP apply to this trial in all sites.

Table 1: Safety Event Definitions

Term	Definition
Adverse Event (AE)	Any untoward medical occurrence in a patient or clinical trial participant administered a medicinal product and which does not necessarily have a causal relationship with this treatment.
Adverse Reaction (AR)	Any untoward and unintended response in a participant to an investigational medicinal product which is related to any dose administered to that participant. This includes medication errors, uses outside of protocol (including misuse and abuse of product).
Serious Adverse Event (SAE), Serious Adverse Reaction (SAR) or Unexpected Serious Adverse Reaction	Any adverse event, adverse reaction or unexpected adverse reaction, respectively, that: 
 ● results in death, ● is life-threatening*, ● requires hospitalization or prolongation of existing hospitalization**, ● results in persistent or significant disability or incapacity, or ● consists of a congenital anomaly or birth defect

* A life- threatening event, this refers to an event in which the participant was at risk of death at the time of the event; it does not refer to an event which hypothetically might have caused death if it were more severe.
 
** Hospitalization is defined as an in-patient admission, regardless of length of stay. Hospitalization for pre-existing conditions, including elective procedures do not constitute an SAE.
	
Suspected Unexpected Serious Adverse Reaction (SUSAR)	An unexpected adverse reaction which is also categorized as serious.
Important Medical Event	These events may jeopardize the participant or may require an intervention to prevent one of the above characteristics/consequences. Such events should also be considered 'serious'.

In addition to the definition above, Adverse Events (AEs) include but are not limited to the following:

- an exacerbation (i.e. increase in the frequency or intensity) of a pre-existing illness, episodic event or symptom (initially observed at the screening), that is detected after IMP administration/trial intervention
- Occurrence of a new illness, episodic event or symptom, that is detected after IMP administration/trial intervention

AEs do NOT include:

- Medical or surgical procedures: the condition that leads to the procedure is the AE
- Pre-existing disease or a condition present before treatment that does not worsen
- Hospitalization where no untoward or unintended response has occurred e.g. elective cosmetic surgery
- Overdose of medication without signs or symptoms

9.2 Procedures for recording and reporting of adverse events (AEs) and serious adverse events (SAEs)

Non-serious AEs as well as SAEs will be self-reported by the participant via online platform or SMS system. Participants are requested to provide details of any symptoms they have experienced and details of any hospitalizations. The investigator will be notified by the online system of all events self-reported by the participant in order to perform their assessment of the event and complete the 'Investigator Adverse Event Report. If the participant becomes very unwell, they will not be able to respond to the weekly SMS messages. As long as they have given consent for an alternative contact to be contacted (in line with local data protection requirements), the alternate contacts will be contacted. If the alternative contact confirms that the participant is unwell, or if they cannot be contacted, the site PI will be informed. The PI or delegate will investigate, assess the event and complete an AE form, called 'Investigator Adverse Event Report' on the online system, immediately and no later than within 24 hours if the event meets SAE criteria.

A notification will be also sent to the sponsor for all AEs meeting serious criteria, including those self-reported by the participant or assessed as SAEs by the PI or delegate. Treatment should be discontinued in line with Section 8.5. Automated reminders will be sent to participant or investigator if safety event related forms are not completed in the expected timelines.

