9.3 Assessments of Adverse Events

Adverse events will be assessed for causality, seriousness and expectedness as described below.

9.3.1 *Seriousness assessment*

When an AE occurs, the investigator will confirm if the event is serious as per the definition given in section 9.1. If the self-reported adverse event details provided by the participant are not sufficient for the investigator to make an assessment, they will contact the participant for further information. If the event is classified as 'serious' then additional information may be requested to be completed by the participant to aid in the assessment of causality.

9.3.2 *Severity assessment*

The investigator will assess all SAEs for severity. Where possible the system used by CTCAE (Common Terminology Criteria for Adverse Events) v5.0 27-Nov-2017 should be used for event name and severity as outlined here:

Table 2: Severity Grade Definitions

GRADE 1 MILD	GRADE 2 MODERATE	GRADE 3 SEVERE	GRADE 4 POTENTIALLY LIFE THREATENING	GRADE 5 DEATH
Mild; asymptomatic or mild symptoms; clinical or diagnostic observations only	Moderate; minimal, local or noninvasive intervention indicated; limiting age appropriate instrumental ADL	Severe or medically significant but not immediately life-threatening; hospitalization or prolongation of hospitalization indicated; disabling; limiting self-care ADL	Life-threatening consequences; urgent intervention indicated	Death related to AE

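### The SAE footnote on hospitalization for pre-existing conditions is unqualified and contradicts the AE definitions, so an admission for a post-dose exacerbation can miss expedited handling

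*Combined protocol and SAP*

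**What the plan says.** Table 1 in section 9.1 defines an SAE as an AE that meets any one of several criteria. One is that the event "requires hospitalization or prolongation of existing hospitalization". A footnote marker sits on that criterion. The footnote first defines hospitalization as an in-patient admission of any length, and then adds: "Hospitalization for pre-existing conditions, including elective procedures do not constitute an SAE".

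The text below the table says that AEs include "an exacerbation (i.e. increase in the frequency or intensity) of a pre-existing illness, episodic event or symptom" when this is detected after the IMP or trial intervention. Two entries in the list of what is not an AE also bear on the point: "Pre-existing disease or a condition present before treatment that does not worsen", and "Hospitalization where no untoward or unintended response has occurred e.g. elective cosmetic surgery".

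Table 1 has a separate row for important medical events, which may put the participant at risk or need action to avert one of the listed outcomes. Of these it says: "Such events should also be considered 'serious".

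Section 9.3.1 tells the investigator to confirm seriousness by the section 9.1 definition. Section 9.2 requires the investigator's report "immediately and no later than within 24 hours if the event meets SAE criteria". Section 9.3.2 states: "The investigator will assess all SAEs for severity".

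**The concern.** The footnote mentions elective procedures only as an example, so they do not limit its reach. Nothing in it requires that the admission was planned or that the condition is unchanged. Take a participant with known asthma, diabetes or coronary disease who is admitted unplanned with a flare after dosing. Under the exacerbation bullet and the main definition this is an AE that required admission, hence an SAE. Under the footnote it is an admission for a pre-existing condition, hence not an SAE.

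Such participants are expected. Section 11.4.2 lists coronary disease, diabetes, hypertension, respiratory disease and HIV among the variables for additional analyses. The trial is run remotely without follow-up visits (section 3.1) and AEs are self-reported (section 9.2). The SAE pathway is therefore the main prompt check on an event by someone outside the site. What is at stake is whether worsening of a participant's existing disease after an IMP reaches the sponsor and, if related and unexpected, the regulators on the expedited timetable. Consistency across sites in nine named countries is also at stake.

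**Working it through.** No arithmetic applies. The check sets the passages side by side and traces one event through them.

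**1. Does the footnote have a harmless job to do?** Under Table 1 an event must be an AE before it can be an SAE. Unchanged pre-existing disease, and admissions with no untoward response such as elective surgery, are already listed as not being AEs. They cannot be SAEs whether or not the footnote exists. Its main independent effect therefore falls on admissions that *are* AEs, chiefly exacerbations of pre-existing illness. Those are the admissions that the bullet below the table brings in.

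**2. What happens to an unplanned admission for a post-dose exacerbation?** Suppose that hospitalization is the only seriousness criterion met and that the site follows the footnote literally.

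| Step | Trigger in the protocol | Outcome |
|---|---|---|
| AE recording; investigator notified | Any self-reported event (9.2) | Still applies |
| Seriousness confirmation | Section 9.1 definition (9.3.1) | Done, but answer is non-serious |
| Causality | All AEs (9.3.3) | Still applies |
| Expectedness | Possible involvement of the intervention (9.3.4) | Still applies if possibly related |
| 24-hour investigator report | SAE criteria met (9.2) | Not triggered |
| Sponsor notification through the investigator | Serious criteria met (9.2) | Not triggered |
| Severity assessment | SAEs (9.3.2) | Not triggered under 9.3.2 |
| Clinical Reviewer review | SAE reports (9.4) | Not triggered |
| SUSAR status | A serious adverse reaction judged unexpected (9.3.4) | Not available |

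Two entries need qualifying. Section 9.2 also mentions sponsor notification of serious events that the participant self-reports, so that route may stay open. Section 11.1.2 describes CTCAE grading of adverse events as the safety outcome, so grading is not clearly lost altogether.

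**3. Which routes to seriousness does the footnote leave alone?** It qualifies the hospitalization criterion only. Death, life-threatening events, persistent disability and birth defects are untouched, and so is the important-medical-event row. That row depends on judgement, however, and an investigator using it for an ordinary admission has to set it against an express statement that the admission is not an SAE.

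**4. Size.** The documents give neither the prevalence of pre-existing conditions nor an admission rate. IMP-specific exclusions (section 7.1.2, criterion 7) would alter both. No defensible count follows.

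**The case against.** The best defence is that the footnote can be read charitably. A flare after dosing is an AE in its own right, so the admission is for that AE, and the footnote concerns only the unchanged background condition. That reading fits the two AE exclusions, and an experienced investigator may well adopt it. It stands to this extent: the text is contradictory, and exclusion from SAE handling is a possible result, not a settled one. It does not clear the footnote, because on that reading the sentence adds nothing to exclusions already present, and nothing in its wording directs a site to it.

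Four stronger conclusions are tempting, and the documents do not support them:

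- *Hospitalization for a pre-existing condition can never be an SAE.* The footnote qualifies one criterion. The other criteria and the important-medical-event row can still make the event serious.
- *All later safety handling is lost.* Causality covers all AEs, and expectedness covers any possibly related event. Participants are also asked about hospitalizations (section 9.2). Section 16 provides for reporting of unanticipated problems and for DMC review of safety data.
- *The comparison of SAEs between arms would be biased.* Sections 11.1 to 11.6 specify no such comparison. The same definition applies to every arm, and nothing shows differential misclassification.
- *A stated number of events would be missed.* Any figure would rest on invented rates and on every site taking the literal reading.

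**Conclusion.** The point holds in a limited form. The footnote is wrong as written: followed literally, it takes out of the SAE definition a kind of event that the same section counts as an AE and that meets a listed seriousness criterion. The effect is confined to admissions for post-dose worsening of a pre-existing condition that are serious through hospitalization alone. For those, the 24-hour report, investigator-triggered sponsor notification, section 9.3.2 severity assessment, Clinical Reviewer review and SUSAR status can be missed, and classification can differ between sites.

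This rests on two assumptions: that some sites apply the footnote as worded, as section 9.3.1 tells them to, and that no other seriousness criterion is met. The number of events cannot be derived from the documents. The primary endpoint is unaffected. The passages should be reconciled because the defect lies in the definition that triggers expedited safety reporting and is cheap to correct.

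**What to change.** Replace the last sentence of the footnote with text to this effect: *Hospitalization (for example elective or pre-planned) for a pre-existing condition that has not worsened since enrolment, and with no untoward occurrence, does not constitute an SAE. Any hospitalization, planned or unplanned, for worsening of a pre-existing condition after IMP administration meets the hospitalization criterion.*

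This carries the two qualifiers of the AE exclusion list into the footnote and covers all four combinations:

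- Planned or unplanned admission, condition worsened after IMP administration: meets the criterion.
- Planned or unplanned admission, condition unchanged and nothing untoward: excluded.

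An untoward occurrence during an otherwise excluded admission is assessed as an AE in the usual way. The sponsor should also check that the start point, enrolment or IMP administration, is used consistently in the footnote and the AE bullets. Any eCRF seriousness question or site guidance that repeats the definition should match.

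The cost is one amended footnote, any matching guidance, and a modest number of additional SAE reports to process.
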